A novel adaptation of the Look AHEAD intervention for the purpose of this study is the addition of a CTS into the intervention, which will allow for tailoring of the intervention to the individual patient. Patients will be encouraged to weigh themselves daily using an electronic scale (provided) that directly uploads data via a cellular signal to a website. We developed computer code that automatically retrieves the data from this website and plots it onto their personal weight graph (**Figure 3**). This weight graph will be available to the patient, his/her health coach, and primary care provider via the CTS over the internet. We have used this approach in other trials, including CALERIE, an intensive 2 y intervention.¹⁰ The CTS will be

used by the health coaches to identify patients who are struggling to meet their weight loss goals, triggering the algorithm to deploy strategies from the “toolbox” (described below). Information from the CTS is also used by the intervention team to observe adherence on a study-wide basis, for each of the clinics, and for each patient. Reports generated from the CTS on session attendance, self-monitoring, dietary adherence, and weight loss serve as indices of adherence to the intervention and are used by the team to evaluate compliance.

We will use a weight loss calculator to:

- 1) calculate personalized daily energy targets for each patient that, if met, will result in 10% weight loss, and 2) create a weight graph that displays each patient’s weight loss over time (see **Figure 3**). This weight graph determines if they are meeting their energy intake target and losing weight at the rate expected. The weight loss calculator was developed by members of this research team and colleagues. The calculator accurately predicts weight loss and accurately estimates the amount of energy intake needed to achieve specific weight loss goals (a version of the calculator can be found at www.pbrc.edu/research-and-faculty/calculators/weight-loss-predictor/).⁴³⁻⁴⁶

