*completed by patients in the active intervention arm only

Parallel Medical Record Data Collection

In addition to the “gold standard” data collection of outcome measurements by the research staff, a parallel data collection effort will be done in PROPEL by utilizing the medical records at the participating clinics. For each of the participating patients in both arms, a retrospective chart review covering the period of the intervention will be done to abstract data on changes in weight and other clinical variables of interest over the course of the intervention. The electronic medical records of the patients will be obtained, or in cases where electronic records are not available, paper medical records will be abstracted by hand and data-entered by research staff.

12. Quality Assurance and Control

Quality assurance and quality control is of utmost importance in a randomized clinical trial. Standardized protocols for all measurements have been developed, and adherence to the written protocols is of paramount importance. All data collection personnel will be certified as competent to make the required measurements by trained experts. The following provides an outline of the quality assurance and control program developed for PROPEL:

- Training and certification of all data collection personnel by experts
- Development of detailed manual of operations
- Retraining and recertification of all data collection personnel twice-yearly
- Maintenance of logs of certified personnel
- Routine calibration of all equipment following manufacturers guidelines
- Maintenance of logs of calibrated equipment
- Performance of routine clinic site-visits and source document verification
- Setting realistic limits on data entry fields in REDCap
- Remote monitoring of data entry, missing data and lag times through REDCap
- Creating both real-time and subsequent executable data quality checks in REDCap
- Querying appropriate personnel regarding missing data
- Preparing quality control reports for personnel, investigators and Data and Safety Monitoring Board

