The usual care arm will receive the obesity treatment currently approved by CMS. A baseline webinar will be conducted with the primary care providers randomized to usual care, describing the current CMS approach to reimbursing for obesity treatment and background on obesity interventions; a reminder informational brochure will be sent to the primary care providers at 1 y. Patients in the usual care arm will receive their normal, usual care from their primary care team, and they will participate in the measurement of the outcomes at 6, 12, 18 and 24 months.

Sources of Materials

Materials will be collected from human subjects in the form of outcome data at a screening visit, at baseline, and at 6, 12, 18 and 24 month assessment visits and will include questionnaire data, anthropometric measurements, blood pressure measurements (not performed at SV), and finger-stick blood samples (baseline, month 12 and month 24 only). We will conduct parallel data collection using the electronic medical records from the participating clinics in addition to data collection by our trained assessment team. We will rely on the primary care staff to track changes in body weight over the course of the intervention. Our study informatics staff will extract data on clinical variables (blood pressure, glucose, cholesterol, etc.) from the electronic medical records in the clinics.

All outcomes will be assessed using validated scales and tests where they exist. For example, height, weight, and waist circumference will be measured using standard procedures. Blood pressure will be measured in all clinics using a validated Omron automated device, and finger-stick blood samples will be used to measure fasting levels of cholesterol, triglycerides and glucose using a validated Cholestech LDX point-of-care device. In addition to direct health measures, several patient-reported outcomes will be measured by questionnaire, including quality of life, functional capacity, and satisfaction with care.

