The focus of the PCORI Funding Announcement under which this study was funded is on obesity reduction in adults therefore the patients in this study are mainly adults (20 - 75 y of age). The treatment of childhood obesity is beyond the scope of this intervention.

15. Power and Sample Size

The sample size calculations for PROPEL were based on LOSS, a pragmatic clinical trial conducted by Pennington Biomedical in eight primary care clinics across the state of Louisiana comparing intensive medical intervention for obesity versus usual care.⁴ According to the 2013 *AHA/ACC/TOS Obesity Guidelines*, as little as 3-5% weight loss is likely to result in clinically meaningful health outcomes.²⁹ The calculations assume that the study will be powered to detect a mean weight loss in the intervention arm of 3.5% at 2 y, relative to usual care, in race- and sex-specific subgroups. We are targeting a mean weight loss of >5% which we anticipate to be 3.5% more than usual care. Both the total and relative weight loss meet currently accepted levels of clinical significance.

Power calculations used a nominal 0.05 significance level with a two-tailed test with minimal power of 80%. Based on the LOSS study, the standard deviation for weight change for patients nested within clinics was 8.4%. For the subgroup analysis, a net sample size of 184 patients (92/arm) is sufficient for detecting a 3.5% weight loss with 80% power when randomization is performed at the patient level. After accounting for the design effect, at least 134 patients per arm are required to realize 80% power in a trial randomized at the clinic level. A previous study in primary care (PROACTIVE) had 20% attrition over 24 months. However, given the challenges of working with a clinic population across an entire state, we have allowed for a conservative estimate of 30% attrition for this trial. Thus, allowing for 30% attrition, at least 192 patients per arm are needed with a total (2 arms) enrollment of at least 384 patients per subgroup analyses.

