Based on data from the patient population served by Louisiana safety net hospitals⁸² and Federally Qualified Health Centers in Louisiana which is approximately 50% African American and 50% female, this translates into a total sample size of at least 768 patients, which will provide at least 97% power to detect a mean weight loss in the intervention arm of 3.5% at 2 y, relative to usual care in the total sample. To account for the increased rate of attrition in Federally Qualified Health Centers, up to 850 participants (425 patients per arm / 47 patients per clinic / 18 clinics) will be enrolled. Although Hispanics will be included in the trial, the low Hispanic population in LA (4%)²¹ precludes sub-group analysis.

16. Data Analysis Plan

To address the primary aim, weight loss will be analyzed as mean percent of baseline weight loss at months 6, 12, 18 and 24 in the context of linear mixed (fixed and random) effects multi-level models. In addition to intervention group, clinics and assessment time, and their interaction terms, the model may include and patient-level (weight, age, sex, race) and clinic-level (clinic size, %African American, % Medicaid/Medicare, etc.) variables as explanatory covariates.

Preliminary analytical findings will be used to choose the most plausible and efficient repeated measures covariance structure (e.g., compound symmetric, autoregressive, unstructured) to use. Although substantial effort will be employed to minimize missing data, it is inevitable that some missing data will occur. An intention-to-treat analysis that includes all randomized patients, regardless of the number of assessments obtained, will be conducted. The primary analysis will use the mixed effects model mentioned above and employ restricted maximum likelihood using all available data. The analytical plans are flexible and will be adapted as scientific perspectives are advanced.

Additional analyses to test the secondary aims are described below:

Secondary Aim 1. Evaluate relationships between adherence to intervention components (physical activity, diet, sessions, etc.) and corresponding changes in body weight and secondary outcomes (post-hoc analyses).

The first secondary aim will be accomplished by conducting analyses of adherence data and changes in the outcomes, and by conducting sub-analyses in different compliant groups (attended at $\geq 80\%$ of sessions, etc.).

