Heterogeneity of treatment effect will be investigated in several subgroup analyses: men vs women, whites vs African Americans, ages 20-44 y vs 45-64 y vs ≥ 65 y. The intervention effect on weight loss will be investigated using a subgroup variable in mixed effects multilevel models analogous to the primary analysis with a focus on intervention-by-subgroup interactions coupled with illustrative graphics. Subsequent analyses will focus on elucidating underlying reasons for the subgroup differences and how these differences influence guidelines that may translate to the general population. Exploratory analyses using fixed and random effects models will determine treatment differences among clinics and estimate the variability associated with these differences.

Significant subgroup heterogeneity in outcome response (e.g., significant sex differences in effectiveness), supported by significance of the test for intervention-by-sex interaction, would lead to further investigation in search of the underlying reasons for the differential response. Previous studies provide evidence that responses to weight loss interventions vary by age, race and sex.⁸³ It is anticipated that these will be confirmed in this trial. Less is known about the influence of clinic-level variables on treatment response; thus, these analyses are considered exploratory.

Handling of Missing Data

Missing data are expected due to drop outs and missed visits. Weight loss is a subject-level variable and missing assessments would influence tests relative to treatment-by-time interactions. The primary analysis described above will employ restricted maximum likelihood using all data. No patients will be deleted from the analysis because of partial data. To assess the sensitivity of results, weight loss will be analyzed using: 1) all patients irrespective of missing data to perform analysis of variance using mixed effects multi-level models with repeated measures; 2) only patients who have completed all assessment visits and have no missing data, to perform analysis of variance employing mixed effects multi-level models with repeated measures; 3) all patients, irrespective of missing data, to conduct analyses using mixed effects multi-level time trend models with random coefficients to capture individual time trends (does not require complete data across time); and 4) multiple imputation.

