Multiple imputation will be employed to perform statistical inferences that properly account for statistical uncertainty due to missingness. Rubin's multiple imputation procedure replaces each missing value with a set of plausible values that represent the uncertainty about the appropriate value to impute.⁸⁴ Missing values are imputed by drawing random samples, and the process is replicated to provide K data sets with pseudo-complete data. Estimates and corresponding confidence intervals will be plotted against K to determine the optimal K to use in subsequent sensitivity analyses. Mean weight loss is estimated for each data set, and the multiple imputation estimator is the average of the individual estimates. The variance of the estimator is estimated from between- and within-imputation variability.⁸⁵ The SAS® procedure PROC MI provides four relevant options for imputation models and will be used in quantifying uncertainty due to missing data.

Statistical summaries will be compiled on the number of patients overall and by arm and who completed study per protocol, did not complete study per protocol, and reasons for not completing. Patient characteristics (age, sex, race, BMI) will be summarized similarly. Multi-level logistic regression will be used to investigate the significance of correlates of failure to complete the study per protocol.

17. Trial Organization

The Principal Investigator will oversee and monitor progress to reach the milestones with decisions concerning short-term goals and the evaluation of longer-term progress being discussed with the research staff via weekly meetings. Broader management of the project will be undertaken by the Project Management Committee, as described below. The research team will be organized into sub-teams of investigators and staff. The overall organizational structure will be reviewed and amended as required.

Project Management Committee

The Project Management Committee will be comprised of the Principal Investigator, selected co-investigators (i.e. Intervention Director, Assessment Director, and Community Engagement Co-Directors), Project Manager and two patient partners. The Project Management Committee will be responsible for overseeing the day-to-day management of the trial, and the Principal Investigator will make adjustments to the approach used by the team to achieve the milestones.

Intervention Team

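### None of the four planned missing-data sensitivity analyses relaxes missing-at-random, so they may miss, and cannot size, bias from dropout that is informative differently in the two arms

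*Combined protocol and SAP*

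**What the plan says.** Section 16 (Data Analysis Plan) makes the primary analysis a mixed-effects model that will "employ restricted maximum likelihood using all available data". Under Handling of Missing Data it lists four sensitivity analyses:

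1. a model using "all patients irrespective of missing data to perform analysis of variance using mixed effects multi-level models with repeated measures";
2. the same kind of model in patients with no missed visit;
3. a time-trend model with random coefficients in all patients;
4. multiple imputation.

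The imputation text describes the standard Rubin procedure and says that "PROC MI provides four relevant options for imputation models and will be used in quantifying uncertainty due to missing data". The options are not named, and no shift, reference-arm or pattern-mixture imputation appears. Non-completion will be counted overall and by arm with reasons, and its correlates modelled.

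On the amount of missing data, Section 15 says "we have allowed for a conservative estimate of 30% attrition for this trial" and notes that "A previous study in primary care (PROACTIVE) had 20% attrition over 24 months".

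Other weights will exist. Section 11 (Parallel Medical Record Data Collection) says that, in both arms, "a retrospective chart review covering the period of the intervention will be done to abstract data on changes in weight". Section 14 (Sources of Materials) adds: "We will rely on the primary care staff to track changes in body weight over the course of the intervention". Section 10 gives intervention patients an "electronic scale (provided) that directly uploads data via a cellular signal to a website". None of these sources is tied to the handling of missed visits.

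**The concern.** A sensitivity analysis for missing data should vary the assumption that cannot be checked. Here that assumption is that, given the observed weights, patients who leave would have gone on like patients who stay. Analyses 1, 3 and 4 keep it. Analysis 2 replaces it with a stricter one. Agreement among the four would say little about whether it holds.

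A difference between arms in why patients leave is plausible. Intervention patients have coach sessions for 24 months, while usual-care patients have newsletters and/or group sessions. Section 10 (Usual Care Arm) itself says success depends on comparable retention. In the trial used for sizing, Section 2 quotes 24-month loss in the intensive arm as 4.9% with baseline carried forward and 9.6% in completers. That gap of 4.7 points exceeds the 3.5-point target. It does not show informative dropout, but it shows how far missing-data handling can move the estimate.

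What is at stake is the size of the effect. The plan defends 3.5 points as clinically meaningful and expects the results to influence funding of obesity treatment.

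**Working it through.** **Inputs from Section 15.** Difference 3.5 points; SD 8.4; two-sided 0.05; 92 per arm with patient-level randomisation; 134 per arm after the design effect; 30% attrition (20% in the earlier study); up to 850 enrolled, 425 per arm, 18 clinics.

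**The plan's own figures.** A two-sample t calculation for 3.5, SD 8.4 and 80% power gives 92 per arm. 134/0.70 = 191.4, so 192. Both reproduce. The implied design effect is 134/92 = 1.457. With 134/9 = 14.9 patients per clinic, the implied ICC is 0.457/13.9 = 0.033; no ICC is stated.

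**Bias formula.** Let d be the share missing at month 24 and δ how much worse the missing patients did than missing-at-random predicts, with I for intervention and C for usual care. The all-data estimate is overstated by d_I·δ_I − d_C·δ_C. With 30% missing in each arm:
- equal δ in both arms: 0;
- δ_I = 2, δ_C = 0: 0.60 too high;
- δ_I = 0, δ_C = 2: 0.60 too low.

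**Assumed scenario: intervention dropouts end at the usual-care mean, usual-care dropout uninformative.** Then δ_I = 3.5 − g, where g is the part of the shortfall that earlier weights already predict. Assume dropout after month 6, log-odds 0, 0.5 or 1 per SD of poorer month-6 loss, and serial correlation ρ between adjacent visits of 0.5, 0.7 or 0.85. The month 6 to month 24 correlation is ρ³ (0.125, 0.343, 0.614). Dropouts lie on average 0, 0.333 or 0.590 SD below the month-6 mean at 30% dropout (0, 0.385, 0.693 at 20%).

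g = 8.4 × ρ³ × that distance; bias = d(3.5 − g); completers minus all-data = g·d/(1 − d).

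Bias, with the completer gap in brackets, at 30%:

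| Log-odds | ρ 0.5 | ρ 0.7 | ρ 0.85 |
|---|---|---|---|
| 0 | 1.05 (0.00) | 1.05 (0.00) | 1.05 (0.00) |
| 0.5 | 0.95 (0.15) | 0.76 (0.41) | 0.53 (0.74) |
| 1 | 0.86 (0.27) | 0.54 (0.73) | 0.14 (1.30) |

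Example, bottom right: g = 8.4 × 0.614 × 0.590 = 3.04; bias = 0.30 × 0.46 = 0.14; gap = 3.04 × 0.30/0.70 = 1.30. At 20% the bias runs from −0.01 to 0.70 and the gap from 0 to 0.89.

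The bias is largest where the gap is zero. The gap depends only on g. If the same dropouts had followed missing-at-random, the gaps would be identical and the all-data bias zero. The completer comparison therefore does not separate biased from unbiased cases.

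A simulation of 18 clinics of 43 with assumed visit means and SDs covered all four analyses for the top row. Overstatement was 1.06–1.08 (all-data), 1.05–1.08 (completers), 1.15–1.21 (random coefficients) and 1.05–1.08 (imputation).

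**Tipping point, total sample.** 850 enrolled and 30% missing leaves 297.5 per arm.
- Design effect 1.457: SE = 8.4·√(2 × 1.457/297.5) = 0.831. With t on 16 df (18 clinics − 2), 2.12 × 0.831 = 1.76, and (3.5 − 1.76)/0.30 = 5.8.
- Design effect rescaled to 297.5/9 = 33.1 per clinic: 1 + 32.1 × 0.0329 = 2.05; SE = 0.987; (3.5 − 2.09)/0.30 = 4.7.

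A true 2.45 (3.5 − 1.05) gives 2.45/0.831 = 2.95 or 2.45/0.987 = 2.48, both above 2.12.

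**Tipping point, race or sex subgroup.** 134 evaluable per arm: SE = 8.4·√(2 × 1.457/134) = 1.24. (3.5 − 1.96 × 1.24)/0.30 = 3.6; with t on 16 df, (3.5 − 2.63)/0.30 = 2.9.

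The tipping points shift the intervention arm only and hold the SE fixed.

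**The case against.** The plan does not neglect missing data. It pays for visits, runs a retention programme for usual care, keeps every patient in the primary model, and summarises non-completion by arm with reasons. Section 16 calls the analytical plans flexible and mentions subsequent sensitivity analyses when choosing the number of imputations, so a further analysis is not ruled out. Analysis 1 can fairly be read as the reference for the other three. A completer gap can hint at outcome-related dropout. All of this stands, but none of it is a pre-specified departure from missing-at-random, and a departure chosen after the results are seen carries less weight.

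The magnitude is also open to challenge. The documents give no dropout by arm and no mechanism. If poorer early responders leave, earlier weights absorb much of the bias and a completer gap appears. A reader might infer that the estimate will be more than a point too high. That is the top of the range and needs dropout unrelated to earlier weight. A reader might also infer that the primary test is at risk of a false-positive result. Hypothesis 1 is directional, and in the scenario above a true 2.45 remains significant, so the plan's figures do not support that for the total sample.

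**Conclusion.** The gap is real and its importance is low to moderate. The pre-specified analyses may fail to show bias from dropout that is informative differently by arm, and none of them can size it. If intervention dropouts end at the usual-care mean and usual-care dropout is uninformative, a reported 3.5 is overstated by about 0.1 to 1.05 points at 30% dropout and about 0 to 0.7 at 20%. Equally informative dropout in both arms gives bias near zero, and worse outcomes among usual-care dropouts would reverse the sign.

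The total-sample conclusion is robust: overturning it takes a shift of about 5.8 points in intervention dropouts (4.7 with the rescaled design effect). Where dropout is unrelated to earlier weights, that means ending 2.3 (1.2) points worse than usual care. The race and sex subgroups have less room. Their tipping shift of 2.9 to 3.6 points is about the same as dropouts ending at the usual-care mean. These figures rest on the implied ICC of 0.033 and on the assumed dropout patterns.

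**What to change.** Keep the primary model and the four planned analyses. In Section 16, Handling of Missing Data, pre-specify two more analyses of missing month-24 weight:

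- **Tipping point.** Multiple imputation with a shift δ added to imputed values, varied separately by arm from 0 until the conclusion changes. Report it for the total sample and the race and sex subgroups.
- **Control-based multiple imputation.** Report it beside the primary result as a conservative bound, not as a replacement.

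Include arm, earlier visit weights and clinic in the imputation model. Section 14 (Pregnancy and Other Exclusions) removes data after conception for some pregnancies. Do not apply either method to those data, and state how they are handled. Where available, chart weights can serve as auxiliary data and home-scale weights can inform the range of δ for the intervention arm. The documents do not show how many dropouts will have either, so both should stay optional.

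The cost is a little more programming and no new data collection. The downside is one result that is too low if missing-at-random holds: when dropout is unrelated to earlier weights, by 0.20 × 3.5 = 0.70 to 0.30 × 3.5 = 1.05 points. The report should say so.
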